## CONFIDENTIAL

204837

Objectives	Endpoints

 
To compare the effect of daprodustat administered three-times weekly to epoetin alfa on BP
 
	
 
Change from baseline in SBP, DBP and mean arterial pressure (MAP) at Week 52 and at the end of study treatment
 
Number of BP exacerbation events per 100 patient years
 
N (%) with at least one BP exacerbation event during study
 

 
To generate pharmacokinetic parameters of daprodustat and predominant metabolites following three-times weekly dosing
 
	
 
Plasma daprodustat, M2, M3, M4, M5, M6 and M13 PK parameters pre-dose trough (Ctau) and Cmax
 

 
To compare daprodustat administered three-times weekly to epoetin alfa on global symptom severity and change
 
	
 
Change from Baseline at Weeks 8, 12, 28, and 52 in PGI-S
 

Exploratory Objectives (no statistical testing planned)	Exploratory Endpoints

 
To evaluate graphical relationships between exposure parameters and selected efficacy endpoints of daprodustat administered three-times weekly
 
	
 
Extrapolated Cmax of daprodustat vs. the percent time within the Hgb target range during the EP
 
Extrapolated Cmax of daprodustat vs. mean Hgb over the 52-week treatment period
 
Mean weekly daprodustat dose over 52 weeks vs. the percent time within the Hgb target range during the EP
 
Mean weekly daprodustat dose over 52 weeks vs. mean Hgb over the 52-week treatment period
 


 
To evaluate graphical relationships between daprodustat administered three-times weekly against MACE and the combined safety endpoint of MACE + thromboembolic event + hospitalization for Congestive Heart Failure (CHF)
 
	
 
Extrapolated Cmax of daprodustat in participants without MACE compared to those with MACE (as well as for the combined safety endpoint of MACE + thromboembolic event + hospitalization for CHF)
 
Mean weekly daprodustat dose in participants without MACE compared to those with MACE (as well as for the combined safety endpoint of MACE + thromboembolic event + hospitalization for CHF)
 

 
To compare the effect of daprodustat administered three-times weekly to epoetin alfa on BP and BP medication changes
 
	
 
Observed and change from baseline in SBP, DBP and MAP by visit
 
Number of BP medications per participant by visit
 
Change from baseline in the number or dose of BP medications per participant by visit
 
N (%) of participants who had no change in the number or dose of BP medications from baseline by visit
 
N (%) of participants who had an increase in the number or dose of BP medications from baseline by visit
 
N (%) of participants who had a decrease in the number or dose of BP medications from baseline by visit
 

 
To further compare the effect of daprodustat administered three-times weekly to epoetin alfa on Hgb variability
 
	
 
Hgb observed and change from baseline across all visits
 
% of time Hgb is above, within and below the analysis range of 10 to 11.5 g/dL during the EP
 
Number (%) of participants with mean Hgb above, within and below the Hgb analysis range during the EP
 
Number (%) of participants with a Hgb <7.5 g/dL during the EP
 
Number of times Hgb <7.5 g/dL during the EP
 

## CONFIDENTIAL

204837

Objectives	Endpoints
	
 
• Number (%) of participants with a >1 g/dL increase in Hgb within any 2-week period (assessed at Week 2 through Week 8), or with a >2 g/dL increase in Hgb within any 4-week period up to Week 52
 
• Number (%) of participants with a >1 g/dL decrease in Hgb within any 2-week period (assessed at Week 2 through Week 8), or with a >2 g/dL decrease in Hgb within any 4-week period up to Week 52
 
• N (%) of participants with a Hgb value <math>\geq 12</math> g/dL during the EP
 
• Number of times Hgb <math>\geq 12</math> g/dL during the EP
 
• % of time Hgb <math>\geq 12</math> g/dL during the EP
 

 
• To compare the effect of daprodustat administered three-times weekly to epoetin alfa on measures of iron parameters
 
	
 
• Observed and change from baseline in hepcidin, ferritin, transferrin saturation (TSAT), total iron, total iron binding capacity (TIBC) across all visits
 
• Average quarterly ferritin
 
• Average quarterly TSAT
 
• Average quarterly IV iron dose/participant
 
• N (%) of participants who met iron management criteria
 
• N (%) of participants who reduced IV iron supplementation relative to baseline [defined as total iron (mg) over 4 weeks prior to randomization] during EP [defined as average monthly IV iron dose (mg) over Weeks 28 to 52]
 

 
• To compare the effect of daprodustat administered three-times weekly to epoetin alfa on the need for red blood cell (RBC) and whole blood transfusions
 
	
 
• Number (%) of participants who receive at least one RBC or whole blood transfusion by Week 52
 
• Number of RBC and whole blood transfusions per 100 patient years
 
• Number of RBC and whole blood units per 100 patient years
 

 
• Characterize the pharmacodynamic (PD) effect of daprodustat administered three-times weekly on EPO, vascular endothelial growth factor (VEGF) and RBC
 
	
 
• Maximum observed change from baseline in EPO
 
• Maximum observed % change from baseline in VEGF
 
• Change from baseline in hematocrit, RBC count, and reticulocyte count
 


 
• To compare the effect of daprodustat administered three-times weekly to epoetin alfa on lipid parameters.
 
	
 
• Observed and % change from baseline in lipid parameters by visit [total cholesterol, direct low density lipoprotein cholesterol (LDL-C), high density lipoprotein cholesterol (HDL-C)]
 

 
• To evaluate the dose adjustment scheme
 
	
 
• Assigned dose by visit and at Day 1, Week 28, and Week 52
 
• Most recent dose prior to Week 28, Week 52 and end of study treatment
 
• Number (%) of participants with 0, 1, 2, or >2 dose adjustments during the following periods: 
 
○ Day 1 to < Week 28
 
○ Week 28 to < Week 52
 
○ Day 1 to < Week 52
 
 
 
• Number of dose adjustments during the following periods: 
 
○ Day 1 to < Week 28
 
 
 

**CONFIDENTIAL**

204837

Objectives	Endpoints
	
 
○ Week 28 to < Week 52
 
○ Day 1 to < Week 52
 
● Number of dose adjustments per year during Day 1 to < Week 52
 
● Time dose held for Hgb <math>\geq 12</math> g/dL
 

 
● To further compare daprodustat administered three-times weekly to epoetin alfa on global symptom severity and change
 
	
 
● Shift tables (Baseline to Weeks 8, 12, 28, and 52) in PGI-S
 
● N (%) of participants within each PGI-C symptom change level at Weeks 8, 12, 28, and 52
 

1. Hgb change from baseline to Week 52 is tested for non-inferiority, using the -0.75 g/dL margin used in the primary analysis. % time in range is tested first for non-inferiority, then for superiority. The non-inferiority margin for % time in range is defined in Section 7.3.1.

## 2.3. Study Design

Overview of Study Design and Key Features	

The diagram illustrates the study design timeline. It begins with a 4-week Screening Period. This is followed by a 52-week Treatment Period, which is divided into a Stabilization Period (Day 1 to Week 28) and an Evaluation Period (Week 28 to Week 52). During the treatment period, participants receive Daprodustat three-times weekly and Epoetin Alfa. The goal is to achieve and maintain hemoglobin (Hgb) levels between 10 to 11 g/dL. The study concludes with a Follow-up Period of 4 to 6 weeks after the last dose. Randomization occurs at Day 1 with a 2:1 ratio of daprodustat to epoetin alfa. The total number of participants is approximately 402.
 
Randomization (Day 1) N≈402
 
End of Treatment (Wk 52)
 
Screening Period: 4 weeks
 
Treatment Period (52 Wks):
 
 
Stabilization Period: Day 1 to Wk 28
 
Evaluation Period: Wk 28 to Wk 52
 
 
Follow-up Period: 4 to 6 weeks after Last Dose
 
Treatments: Daprodustat Three-times Weekly, Epoetin Alfa
 
Goal: Achieve and Maintain Hgb between 10 to 11 g/dL
 
Randomization: 2:1 daprodustat: epoetin alfa
 
Key Features:
 
 
HD ≥ 3/week
 
Prior rhEPO or analogs
 
Hgb 8 to 11.5 g/dL
 
Hgb efficacy
 
PK/PD
 
Safety (CV)
 
	
Design Features	
 
This is a randomized, double-blind, active-controlled, parallel-group, multi-center study in hemodialysis-dependent participants, including combination methods such as hemodiafiltration or hemofiltration with HD, who have anemia of CKD and are currently treated with rhEPO or its analogs.
 
This study includes a 4-week Screening Period, a 52-week Treatment Period and a Follow-up Period
 
The 52-week Treatment Period consists of: 
 
The Stabilization Period (SP), defined as the period from Day 1 to Week 28 (up to but excluding the Week 28 visit), during which study treatment will be dose-titrated to achieve and maintain Hgb in the target range.
 
The Evaluation Period (EP), defined as the period from Week 28 to Week 52, to assess long-term efficacy and safety. The study treatment may be dose-titrated, if needed, during this period to achieve or maintain Hgb level in the target range.
 
 
 
Each participant will remain in the study for up to 62 weeks, including screening through the follow-up period. Participants who permanently discontinue study treatment will remain in the study.
 

Treatment Assignment	
 
The randomization schedule will be computer generated by Pharmaceutical Product Development, LLC (PPD) prior to the start of the study, using the validated randomization system Prism. Participants will be randomized centrally using an Interactive Response Technology (IRT) system.
 
Randomization will be stratified by region. Following stratification, participants will be randomized 2:1 to daprodustat or epoetin alfa. Daprodustat will be administered three-times weekly and epoetin alfa will be administered once weekly or three-times weekly, depending on dose level.
 
Due to the difference in formulations between the investigational product and the active control (tablets versus IV injection), and in order to maintain the study blind,
 

Overview of Study Design and Key Features	
	each participant will receive a tablet and an IV study treatment; one will be active and one will be inactive. Participants randomized to receive daprodustat will also receive saline IV injection. Participants randomized to receive epoetin alfa will also receive placebo tablets.
Dosing	
 
The dose of both study treatments will be adjusted in order to maintain Hgb concentration in the target range (10.0 to 11.0 g/dL). Adjustment of both study treatments (tablets and IV injection formulation) will follow a protocol-specified study treatment dose adjustment algorithm to achieve and maintain Hgb within the target range of 10.0 to 11.0 g/dL, inclusive. Dose changes will be made programmatically by the Interactive Response Technology (IRT) system for both study treatment arms. Please refer to the protocol for starting doses, dose steps, dose adjustment algorithm, and temporary study treatment interruption.
 

Time & Events	
 
Refer to Section 14.2. Appendix 2: Schedule of Activities
 

Interim Analysis	
 
There are no plans to evaluate interim data for the purposes of stopping based on Hgb efficacy data.
 
The IDMC will periodically receive unblinded safety reports containing clinical endpoints (whether adjudicated or pending adjudication) and SAEs, from an independent Statistical Data Analysis Center (SDAC) while Phase 3 studies with daprodustat are ongoing. The IDMC may recommend stopping this study for safety at any time.
 

## 2.4. Statistical Hypotheses

The primary Hgb efficacy objective will assess the estimand defined as the effect of daprodustat treatment relative to rhEPO on the change in Hgb from baseline to the average of all values in the EP, regardless of adherence to treatment including interruptions and discontinuations, the use of non-randomized ESA medication for any reason including rescue therapy, or the use of blood transfusions, in subjects on dialysis currently treated with an ESA with anemia secondary to CKD and assuming subjects do not die before the end of the EP. The analysis will test whether daprodustat is non-inferior to rhEPO according to the following statistical hypotheses:

- Null: The difference in mean change in Hgb between baseline and EP, between treatment arms (daprodustat-epoetin alfa), is less than or equal to -0.75 g/dL.
- Alternative: The difference in mean change in Hgb between baseline and EP, between treatment arms (daprodustat-epoetin alfa), is greater than -0.75 g/dL

The non-inferiority margin is pre-defined as -0.75 g/dL. This margin was selected to be consistent across all clinical trials in the daprodustat Phase 3 clinical development program in participants with anemia of chronic kidney disease, and it was determined based upon a combination of clinical judgment, statistical reasoning and regulatory guidance for designing non-inferiority trials.

Statistical significance of non-inferiority will be assessed at the one-sided 2.5% level. An analysis of covariance (ANCOVA) model including randomization stratification factor, baseline hemoglobin and treatment will be used to obtain a point estimate and the two-

**CONFIDENTIAL**

204837

sided 95% confidence interval (CI) for the treatment difference (daprodustat-rhEPO) and generate the p-value for the non-inferiority test. The non-inferiority p-value will show strength of evidence against the null hypothesis. Non-inferiority will be established if the lower limit of the two-sided 95% CI for the treatment difference is greater than -0.75 g/dL.

### 3. PLANNED ANALYSES

#### 3.1. Interim Analyses

The IDMC will periodically receive unblinded safety reports containing, at a minimum, clinical endpoints (whether adjudicated or pending adjudication) and SAEs, from an independent Statistical Data Analysis Center (SDAC) while the study is ongoing. The IDMC may recommend stopping the study for safety at any time. (See IDMC charter for further details).

There are no plans to evaluate interim data for the purposes of stopping based on Hgb efficacy data.

#### 3.2. Final Analyses

The final planned primary analyses will be performed after the completion of the following sequential steps:

1. The end of the study has been reached, as defined in the protocol.
2. All required database cleaning activities have been completed and final database release (DBR) and database freeze (DBF) has been declared by Data Management.
3. All criteria for unblinding the randomization codes have been met.
4. Randomization codes generated by the Pharmaceutical Product Development, LLC (PPD) have been distributed according to GSK and PPD procedures.

### 4. ANALYSIS POPULATIONS

Inclusion in any analysis population is contingent on a subject signing informed consent.

Population	Definition / Criteria	Analyses Evaluated
Screened	
 
• All participants who sign the ICF
 
	
 
• Study Population
 

All Randomized (ITT)	
 
• All randomized participants. This is the primary population for Hgb efficacy analyses. Participants will be analysed according to the treatment to which they were randomized.
 
• Any participant who receives a treatment randomization number will be considered to have been randomized.
 
	
 
• Study Population
 
• Efficacy
 
• Selected Safety
 

Enrolled	
 
• All participants who passed screening and entered the study. For this study, the Enrolled and All Randomized (ITT) populations will be identical. (Note: Use of enrolled population is required for some displays.)
 
• Subjects will be analysed according to the treatment to which they were randomized.
 
	
 
• Study Population
 

Safety	
 
• All randomized participants who take at least 1 dose of study treatment. Participants will be analyzed according to the treatment they actually received.
 
	
 
• Safety
 

Per-Protocol (PP)	
 
• All ITT participants who do not have PP population exclusions. This population will be the basis for a supportive analysis of the primary efficacy parameter.
 
	
 
• Efficacy
 

Population	Definition / Criteria	Analyses Evaluated
	
Participants will be analyzed according to the treatment to which they were randomized.
 
 
Protocol deviations that would exclude participants from the PP population are defined in Appendix 1: Protocol Deviation Management and Definitions for Per Protocol Population.
 
The PP set will not be analyzed if this population comprises more than 80% of the All Randomized (ITT) population.
 
	
Pharmacokinetic (PK)	
 
All randomized participants for whom a post-baseline PK sample was obtained and analyzed. This will be the population used for all the PK displays.
 
	
 
PK
 

[1]: Only subjects receiving incorrect study treatment for the duration of their study participation will be analyzed according to the treatment received. Otherwise, subjects will be analyzed according to the treatment to which they were randomized.

Refer to [Appendix 10: List of Data Displays](#) which details the population used for each display.

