10.1. Sample Size Determination

10.1.1. Sample Size Assumptions

The size of this study has been determined to be sufficient to meet the ICH E1 guideline for participant exposure, number and duration and to provide at least 90% power to test the primary non-inferiority hypothesis with a two-sided 95% CI.

Approximately 402 participants are planned to be randomized in a 2:1 ratio to daprodustat or rhEPO (268 to the daprodustat arm and 134 to the rhEPO arm), in order to provide at least 100 participants exposed to daprodustat for one year. Participants will be treated to achieve and maintain Hgb between 10 and 11 g/dL. The expected difference in mean Hgb change from baseline and the EP, between arms, is 0 g/dL and the anticipated between participant standard deviation (SD) is 1.5 g/dL, based on historical rhEPO trials and daprodustat clinical trial experience to date. With a prespecified non-inferiority margin of -0.75 g/dL, a two-sample T-test and assuming that up to approximately 10% of

participants will have no Hgb values measured during the EP, 402 randomized participants will provide >90% power to test the primary hypothesis.

With 402 randomized participants, it is anticipated that the difference in mean Hgb change from baseline between arms will be estimated with a precision of 0.33 g/dL (half width of the two-sided 95% CI) and the largest (most negative) difference between arms that would meet the statistical criterion for non-inferiority would be -0.42 g/dL.

Note: Country-specific requirements for France for the sample size consideration are provided in [Appendix 8](#) (see Section 12.8.1, Item 2 for details).

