10.2. Populations for Analyses

For purposes of analysis, the following populations are defined:

Population	Description
Screened	All participants who sign the ICF
All Randomized (ITT)	All randomized participants. This is the primary population for Hgb efficacy analyses. Participants will be analyzed according to the treatment to which they were randomized. Note: While the primary analysis of the primary parameter will exclude those randomized participants who do not have at least one Hgb assessment during the EP, the sensitivity analysis to define the “tipping point” as described in Section 10.3.1 will include all randomized participants.

Population	Description
Per-Protocol (PP)	All ITT participants who are not major protocol violators. This population will be the basis for a sensitivity analysis of the primary efficacy parameter. Participants will be analyzed according to the treatment to which they were randomized. Details will be defined in the RAP.
Safety	All randomized participants who take at least 1 dose of study treatment. Participants will be analyzed according to the treatment they actually received.
PK	All randomized participants for whom a PK sample was obtained and analyzed. This will be the population used for all the PK displays.

Additional populations may be defined in the RAP.

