	
on-treatment Hgb during the EP (this approach corresponds to evaluating an efficacy estimand). A similar “tipping point” analysis as that described above for the primary analysis will be performed for this “on-treatment” analysis. In addition, a supplementary per-protocol analysis will estimate the treatment effect in participants who strongly adhere to the protocol, and sensitivity analyses to explore a shorter EP (Weeks 28 to 36) will be performed for the primary effectiveness estimand and “on-drug” efficacy estimand. Full details of all sensitivity and supplementary analyses will be provided in the RAP.
 
Covariates and Subgroups of Interest: The primary endpoint will be evaluated for a set of pre-specified subgroups to support the proposed indication. Subgroup analyses are aimed to assess for consistency with the overall result, they may have low power if the subgroup is small. Statistical models will be adjusted for the covariates used in the original analysis (randomization stratification factor and baseline hemoglobin), subgroup, treatment and treatment by subgroup interaction. Point estimates and two-sided 95% CIs will be estimated (presented on Forest Plots) and the subgroup by treatment interaction p-value calculated. Subgroup analyses will not be adjusted for multiplicity. Further subgroups/covariates may be defined in the RAP.
 
  
 Category	Subgroups	
   
 Age	<65 years, ≥65 to <75 years, ≥75 years	
 
 Gender	Female, Male	
 
 Race group	American Indian or Alaskan Native, Asian, Black, Native Hawaiian or Other Pacific Islander, White, Mixed Race	
 
 Ethnicity	Hispanic, non-Hispanic	
 
 Region	Regions listed in Appendix 7	
 
 Country	Countries listed in Appendix 7	
 
 Dialysis vintage	0 to <2 years, 2 to <5 years, ≥5 years	
 
 Prior rhEPO dose	<7,000 U/week, ≥7,000 U/week	
 
 rhEPO Hypo-responsiveness	No, Yes (see RAP for definition)	
 
 Baseline Hgb	<9 g/dL, 9 to <10 g/dL, 10 to 11 g/dL, >11 g/dL	
 
 BMI	<30 kg/m², ≥30 kg/m²	
 
 Weight	< 75kg, ≥75kg	
 
 Baseline hsCRP	≤3 mg/L, >3 mg/L	
 
 United States	US, Non-US	
  
 
Additional exploratory subgroups may be defined in the RAP. Additional subgroup analysis for other study endpoints may be performed, and will be defined in the RAP.
	Category	Subgroups	Age	<65 years, ≥65 to <75 years, ≥75 years	Gender	Female, Male	Race group	American Indian or Alaskan Native, Asian, Black, Native Hawaiian or Other Pacific Islander, White, Mixed Race	Ethnicity	Hispanic, non-Hispanic	Region	Regions listed in Appendix 7	Country	Countries listed in Appendix 7	Dialysis vintage	0 to <2 years, 2 to <5 years, ≥5 years	Prior rhEPO dose	<7,000 U/week, ≥7,000 U/week	rhEPO Hypo-responsiveness	No, Yes (see RAP for definition)	Baseline Hgb	<9 g/dL, 9 to <10 g/dL, 10 to 11 g/dL, >11 g/dL	BMI	<30 kg/m ² , ≥30 kg/m ²	Weight	< 75kg, ≥75kg	Baseline hsCRP	≤3 mg/L, >3 mg/L	United States	US, Non-US

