
 
• The while on treatment evaluable Hgb analysis and summaries described above (with the exception of the missing data summary) will also be performed using the PP population and evaluable Hgb values (see Section 14.6.3).
 
• The LS mean treatment difference and associated two-sided 95% CI from this analysis will be included on a forest plot with the primary Hgb analysis results
 

Alternative EP (Week 28-36) Analysis

 
• The following analyses will be repeated using an alternative EP from Week 28-36: 
 
○ The primary analysis and summaries (using on- and off-treatment, observed and imputed, Hgb values (see Section 14.6.3)
 
○ Supportive analyses and summaries of the alternative estimand that uses evaluable Hgb values and a while-on-treatment strategy for handling intercurrent events will be repeated using an alternative EP from Week 28-36.
 
 
 
• Summaries of imputed/missing Hgb values will not be repeated.
 
• The LS mean treatment difference and associated two-sided 95% CI from these analyses will be included on a forest plot with the primary Hgb analysis results.
 

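### The SAP cancels the supportive per-protocol analysis when the per-protocol set exceeds 80% of ITT, in conflict with its own methods section and the protocol, and does not log the change

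*SAP*

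**What the plan says.** The condition stands in the population table of SAP section 4: "The PP set will not be analyzed if this population comprises more than 80% of the All Randomized (ITT) population". It comes with no reason and no requirement on each arm. The same table row gives the PP set its role: "This population will be the basis for a supportive analysis of the primary efficacy parameter".

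Elsewhere the analysis carries no size condition:

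- Protocol 10.2: "This population will be the basis for a sensitivity analysis of the primary efficacy parameter".
- Protocol 10.3.1: "a supplementary per-protocol analysis will estimate the treatment effect in participants who strongly adhere to the protocol".
- SAP 7.1.5.1, under PP Population Analysis: the on-treatment evaluable-Hgb analysis "will also be performed using the PP population and evaluable Hgb values", with its result on the forest plot.
- SAP 14.10.6 and 14.10.7 list Tables 2.014 to 2.016 and Figures 2.006 and 2.007 for the PP set, and Figure 2.003 includes the PP result.

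Table 1 in SAP 2.1, which records departures from the protocol, does not mention the condition, although it records a change as small as renaming a PK trough parameter.

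**The concern.** The primary estimand in SAP 7.1.4 follows a treatment policy for every intercurrent event except death: Hgb counts after discontinuation, non-randomized ESA, rescue and transfusion. In a non-inferiority comparison such events can draw the arms together and favour a pass. A PP analysis is a customary, if imperfect, check on this.

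The rule works against that purpose. It keeps the PP analysis when at least a fifth of participants are excluded and post-randomization selection is heaviest. It drops the analysis when the PP set is larger and easier to interpret. The rule cannot be read as skipping a near-duplicate of ITT, because up to a fifth of participants may differ between the sets. The condition also looks at the total only, so a one-sided pattern of exclusions would not stop the cancellation.

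At stake is a supportive check, and a SAP that gives two instructions for one analysis.

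**Working it through.** **Inputs.** SAP 2.4: "The non-inferiority margin is pre-defined as -0.75 g/dL" and "Statistical significance of non-inferiority will be assessed at the one-sided 2.5% level". Protocol 10.1.1: "The expected difference in mean Hgb change from baseline and the EP, between arms, is 0 g/dL", SD 1.5 g/dL, 268 and 134 randomized, up to about 10% without Hgb in the evaluation period. Protocol 5.2: about 360 evaluable.

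**The plan's own figures.** With 240 and 120 evaluable, SE = 1.5 × √(1/240 + 1/120) = 0.168. The 95% half-width is 0.33, the most negative passing estimate is -0.75 + 0.33 = -0.42, and power at a difference of 0 is 99.4%. These agree with protocol 10.1.1 and with the cell above 99% in 10.1.2.

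**Reach of the rule.** The denominator is all randomized: 0.80 × 402 = 321.6, so the analysis is cancelled at 322 or more, that is with up to 80 excluded. If all 80 were on epoetin alfa, 54 of 134 (40%) of that arm would remain and the half-width would be 0.44. If all were on daprodustat, 188 of 268 (70%) would remain, with half-width 0.33.

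**Precision of PP at the threshold.** With about 215 and 107 participants the half-width is 0.349, the most negative passing estimate is -0.40, and power at a difference of 0 is 98.8%. Low power is therefore no reason to cancel.

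**Illustration of discordance.** Assume SD 1.5, the same endpoint in both sets, an equal fraction f retained in each arm, and no treatment difference in those excluded. Then ITT difference = f × PP difference.

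| PP share of 402 | n per arm | PP half-width | PP fails at or below | ITT difference at that point (× f) |
|---|---|---|---|---|
| 81% | 217 : 109 | 0.346 | -0.404 | -0.327 |
| 90% | 241 : 121 | 0.329 | -0.421 | -0.379 |

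ITT passes down to -0.42 by the plan's figure, so the discordant band is about -0.33 to -0.42 at 81% and about -0.38 to -0.42 at 90%. At the edge, an ITT difference of -0.42 gives PP -0.42 / 0.81 = -0.519, with lower limit -0.519 - 0.346 = -0.865, about -0.87. If all 402 counted at full information, the ITT limit would be about -0.44 and the bands slightly wider.

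**How often.** With PP at 80% of both arms and 402 in ITT, the PP estimate varies around the ITT estimate with SE 1.5 × √[(1/268 + 1/134) × (1/0.8 - 1)] = 0.079. Simulating the two verdicts jointly (400,000 draws) gives the probability that ITT passes and PP fails:

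| True ITT difference | Exclusion unrelated to outcome | Treatment difference 0.5 g/dL higher in the excluded than in the retained |
|---|---|---|
| 0 | 1.0% | 4.1% |
| -0.1 | 3.1% | 11.2% |
| -0.2 | 7.1% | 21.7% |
| -0.3 | 11.3% | 30.7% |

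With SD 1.0 (an assumption) and exclusion unrelated to outcome, the figures are below 0.1% at 0, 0.3% at -0.2 and 2.3% at -0.3.

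**What the retained analysis covers.** Evaluable Hgb (SAP 14.6.3.1) drops off-treatment values and values within 8 weeks after a transfusion or non-randomized ESA. Set against the exclusions in SAP 14.1.1, it does not remove participants for criterion 01 (entry Hgb), 02 (fewer than 5 of 7 evaluable values), 03 (non-compliance) or 04 (inadequate iron status).

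**The case against.** The case for leaving the rule alone has weight.

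- A reader might infer that the rule removes the only analysis able to expose a failure among adherent participants. The documents do not support that. The while-on-treatment analysis runs whatever the PP size, covers discontinuation, rescue and transfusion, and has its own tipping-point, Week 28 to 36 and subgroup versions. What stands is the gap for criteria 01 to 04.
- A reader might add prohibited medication (criterion 05) to that gap. It is largely closed: protocol 8.1 requires permanent discontinuation when more than 14 days of such medication is needed, so later Hgb is off-treatment and not evaluable.
- A reader might infer that the trial's conclusion could change. It could not: non-inferiority rests on the ITT primary analysis. A PP failure would not show inferiority either, because the exclusions are mostly post-randomization and partly defined by the outcome data.
- Protocol 10.2 and 10.3.1 leave details to the SAP, and exclusions are reviewed before unblinding, so the threshold cannot be tuned to results. That is fair, but cancelling an analysis goes beyond detail, and it does not reconcile section 4 with 7.1.5.1.
- The rule may never apply. The roughly 10% expected to have no Hgb in the evaluation period already meet criterion 02, and further exclusions could bring PP to 80% or below.

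**Conclusion.** The point holds as a supportive-analysis and consistency defect of low to moderate severity. SAP section 4 conflicts with SAP 7.1.5.1 and with the protocol, the condition is not logged in Table 1, and up to 80 of 402 participants could be excluded with no PP result.

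The numerical consequence is small under the planning assumptions. It becomes material if the true difference is about -0.2 g/dL or lower, or if exclusion is related to the treatment effect. The figures rest on SD 1.5, equal exclusion by arm and one endpoint for both sets. The last is a simplification: the primary analysis uses on- and off-treatment Hgb with multiple imputation, whereas PP uses evaluable Hgb without imputation. The zero treatment difference among those excluded, used for the discordant bands, is likewise an assumption and not a figure from the documents.

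**What to change.** Delete the 80% sentence from SAP section 4 and always run the PP analysis described in 7.1.5.1, labelled as supportive. If the sponsor prefers to keep a condition, it should apply to each arm, be limited to near-complete overlap with ITT, carry a stated reason, be repeated in 7.1.5.1 and be entered in Table 1.

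The cost is producing displays that the SAP already lists (Tables 2.014 to 2.016, Figures 2.006 and 2.007, and the PP line in Figure 2.003). No new data, method or decision rule is needed.
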